### **Statistical Methods (Supplemental)**

The study was designed with overall survival as the primary endpoint. The design provided 80% power, with alpha of 0.05, to detect a hazard ratio of 1.25 between patients receiving multidisciplinary care and serial care. We targeted enrollment of 150 patients on the multidisciplinary arm and 300 patients on the serial care arm, matched by clinical stage (based on the initial diagnostic CT scan), performance status, insurance status, race, and age range. After initiation of the study, it was determined that the individual 1:2 matching strategy was not attaining high level matches within the allotted parallel time frame for the required number of subjects. To accommodate this change the following revisions were made to the statistical methodology. A frequency matching strategy was used based on the matching variables (age, sex, and histology were controlled for as a model covariate for better numerical efficiency). Crude comparisons between groups were made using standard univariate two sample methods. Comparative analyses were then conducted using matching variables as strata, per original design, with the strata now allowing multiple cases and controls per match group (frequency matching). Specifically, analyses were designed based on conditional logistic regression for each binary endpoint and stratified cox proportional hazards models for survival endpoints. Models were further adjusted to include age, sex, and histology in addition to the adjustment for strata described above. For each outcome, additional statistical models were evaluated controlling for matching variables as covariates in unconditional analyses. All analyses were conducted in SAS Version 9.4 (Cary, NC) with a type-I error rate of 0.05.

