Building a Multidisciplinary Bridge Across the Quality Chasm in Thoracic Oncology

NCT02123797

03/09/2015

PCORI SPECIFIC AIM #3 (with process engineering sub-aim) RESEARCH PROTOCOL

Objective(s) of the study

The objective of this study is to provide rigorous evidence of the impact of multidisciplinary care on lung cancer patient outcomes. Multidisciplinary care is a model of care in which patients, their caregivers, and key specialists concurrently and directly evaluate the same patients in the presence of the patients and their informal caregivers, in order to develop evidence-based consensus care plans. Within the Baptist Memorial Health Care system, the Multidisciplinary Thoracic Oncology Program has two components: Primarily, the program is centered in a multidisciplinary clinic, wherein patients and their informal caregivers are seen by multiple specialists at a single appointment time; secondarily, the program includes a multidisciplinary conference, wherein all of the specialists potentially involved in lung cancer care discuss patients referred for presentation and make consensus recommendations for care. This study focuses primarily on the experience and outcomes of care delivered to patients evaluated in the multidisciplinary clinic. However, data from the conference may also be included in some aspects of the study. The goal is to improve the access and quality of thoracic oncologic care delivery within the Baptist Healthcare System.

The project is broken into three specific aims. The first specific aim has already been submitted separately and approved by the Baptist and University of Memphis IRBs. The second specific aim has been deemed exempt from IRB review as a quality improvement measure. The final specific aim is as follows:

Specific Aim #3 - Perform a prospective, matched cohort comparative effectiveness study of patients receiving serial vs. multidisciplinary care, with key patient-centered endpoints (survival, stakeholder satisfaction with the care experience, quality of life, timeliness and stage-appropriateness of care, quality of staging). Serial care is defined as the current system of linear, sequential, referral-based care delivery.

In an exploratory sub-aim, we will use computer simulation modeling provided by a process engineer to retrospectively and prospectively measure and optimize the efficiency of patient flow through the healthcare system.

Background

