We will begin Specific Aim #3 after a 3-month lead in phase, during which we ensure that all performance targets from Specific Aim #2 are being reliably measured. This aim will include administration of a series of patient, caregiver, and provider surveys as well as analysis of the quality benchmarks mentioned above. Specifically, we propose to perform a prospective, matched cohort comparative effectiveness study of eligible patients receiving care within the multidisciplinary environment versus matched controls concurrently receiving usual, serial care in the same healthcare system.

Eligibility criteria:

Multidisciplinary cases will have an untreated but biopsy-confirmed lung cancer diagnosed, preferably within 8 weeks of screening for study eligibility. Therefore, patients will still need either a staging evaluation or selection of first line therapy, the types of decision-making most often required in lung cancer care.

Controls will be selected from the pool of patients receiving usual ('serial') care within the same institution. Two serial care controls will be matched to each multidisciplinary care case. To be eligible for inclusion, a serial care patient must have an untreated biopsy-confirmed lung cancer, diagnosed preferably within an 8 week window surrounding the diagnosis of the case to whom he/she will be matched (4 weeks prior through 4 weeks after the case's diagnosis), and will be matched hierarchically based on several matching criteria: clinical stage, performance status, insurance status, race, and age range.

All multidisciplinary clinic patients will be screened for eligibility before their initial clinic visit. If a patient is determined to be eligible to participate in Specific Aim #3, they will be approached for consent to the study by the clinical research professionals during their initial visit.

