REACH – To evaluate the reach of the multidisciplinary clinic, we will collect extensive data on all patients participating in Specific Aim #3. These data will cover the full timeline of a patient’s care for lung cancer, including details of their history of lung-cancer-related care prompting their entry into the healthcare system, of their experience within the system, of their expected treatment and their actual received treatment, and finally the outcome of their treatment. These data will be analyzed to define the characteristics of multidisciplinary patients versus serial care patients, which will in turn address questions about the reach of the multidisciplinary clinic (i.e., what kinds of patients are likely to come into contact with multidisciplinary care and what kinds of patients do not?).

EFFECTIVENESS – In order to evaluate the effectiveness of the two models of care, we will analyze the data referenced in the Reach component. We will also administer surveys to all participating patients, their caregivers and their clinical providers. We will test our ability to obtain patient, caregiver, and clinical provider feedback using several instruments (specific questions will be drawn from the attached self-report patient, caregiver, and clinical provider measures and tailored to each stakeholder group as appropriate).

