As noted above, extensive data will be compiled that encompasses the full scope of patients' experience of care for lung cancer, from initial discovery to the conclusion of treatment. To evaluate the effectiveness of patient care, extensive analysis will be performed by researchers at the University of Memphis, School of Public Health, (co-investigators on the grant, signed to a Baptist-approved subcontract) with specific attention given to timeliness of care, completeness of staging, surgical resection rate, and stage-appropriate treatment rate. The de-identified, aggregate results of this analysis will be shared with process engineers at the University of Wisconsin-Madison (co-investigators, signed to a Baptist-approved subcontract) who will use computer simulation modeling to map, measure and optimize the efficiency of patient flow through the healthcare system. Finally, the effectiveness of the clinic will be evaluated using survival time as an outcome, using data from institutional records, supplemented by the Social Security Death Index.

ADOPTION – The adoption domain of the RE-AIM framework will focus on the characteristics of physicians who participate (by referring patients into the clinic or directly providing care within the multidisciplinary environment) versus those who do not participate. This information will be collected by comparing multidisciplinary thoracic program referral records to the list of relevant specialty physicians credentialed within the BMHCC catchment area of the multidisciplinary program. Physician characteristics to be compared include demographics (age, gender) and training/practice (specialty area, years of practice, practice setting).

IMPLEMENTATION/MAINTENANCE – will be measured for the multidisciplinary program as a function of Specific Aim #2.

Data or samples to be collected

All patients will be provided a unique database identifier to anonymize research data.

Patient demographics

sex

race

date of birth

- zip code of residence
- health insurance coverage
- clinical assessment
 - performance status
 - family history of cancer
- comorbidities
- smoking history
- additional risk factors

Pre-treatment care experience

- method of detection
- disease related procedures
 - radiographic scans
 - biopsy procedures
 - provider office visits
 - evaluation for chosen treatment modality

Multidisciplinary conference experience

- date of presentation
- details of patient history at time of presentation

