Specific Aim #3 will require descriptive analysis. The percent of benchmark outcomes (Table 1) will be presented. We will use Chi-square test for categorical variables such as thoroughness of staging and treatment selection. T-tests will be used for continuous variables such as timeliness of care (days, logarithm transformed). All analyses may be stratified by race, gender, socio-economic status, and insurance status. Since we will measure the quality of care outcomes regularly during the whole study period, trend analysis will be conducted to monitor the change of these outcome measures. Computer simulation models will be used for pathway optimization analysis. In addition to descriptive analysis, statistical modeling will be the main tool to compare the quality of care and survival between multidisciplinary program and controls, adjusting for measured confounders. As noted, there are three types of outcomes: categorical outcomes such as thoroughness of staging, and receipt of stage-appropriate treatment; continuous outcomes such as timeliness of care, and survival events. In addition, since we will implement matching in the prospective cohort study by entry criterion, clinical staging, performance status, insurance status, race, and age range, matching analysis will be used. Specifically, in the multivariate models, we will use the conditional fixed effects logistic regression for binary categorical outcomes; fixed effects generalized linear model with Gamma distribution and logarithm link for timeliness of care; and fixed effects proportional hazard model for survival analysis. The matching pair indicates the fixed effect. These can be analyzed by commands such as *xtlogit* with *fe* option, or *stcox* with *strata* option in Stata.

Furthermore, because care delivery and treatment differ between patients with stage I/II and stage III/IV, stratified analysis will be conducted by staging groups. Both descriptive analysis and analytical models will be used. However, statistical power may be insufficient for the stratified analysis.

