Models for categorical outcomes: Assuming Y_i represents whether the patient receives stage-appropriate care (yes/no), and G_i represents whether patient is in multidisciplinary program or matched control, and X_i represents other confounders except matching variables. The conditional fixed effect model can be expressed as $\text{Log}(p(Y_i=1)/p(Y_i=0)) = \beta * G_i + \gamma X_i$. Note that intercept and matching variables are not estimated. The exponent of β is the odds ratio of receiving stage-appropriate care between multidisciplinary v. control. For other categorical outcomes, models and interpretations are similar.

Models for timeliness of care: The timeliness of care is measured in days: for example, days from the first diagnostic imaging test (earliest date of chest X-ray or CT scan) to receiving the actual treatment (surgery, chemotherapy, radiation, or hospice care); days from the first diagnostic imaging test to multidisciplinary clinic visit, and days from multidisciplinary clinic visit to treatment commencement. These variables are inherently right skewed and can be fit with Gamma distribution. In the fixed effects generalized linear model, $\text{Log}(\text{days}_i) = \beta * G_i + \gamma X_i$, the shape and scale parameters of the gamma distribution will be empirically determined based on all observations in each group. The exponent of β is the geometric mean difference of days (similar to median difference) between multidisciplinary program and controls.

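### The adjusted models in the SAP leave out comorbidity, which the protocol collects, so residual confounding of the care-model comparison is possible

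*SAP*

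**What the plan says.** The SAP, Statistical Methods (Supplemental), describes three layers of analysis: crude two-sample comparisons; conditional logistic and stratified Cox models with the matching variables as strata; and further adjustment of those models. On the last it says "Models were further adjusted to include age, sex, and histology in addition to the adjustment for strata described above". It adds that for each outcome "additional statistical models were evaluated controlling for matching variables as covariates in unconditional analyses". Comorbidity is not named in any layer.

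The protocol bears on this in four places:

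- **Eligibility criteria.** The matching variables are "clinical stage, performance status, insurance status, race, and age range". Comorbidity was never one of them.
- **Data or samples to be collected.** The list includes "comorbidities" as an item separate from performance status.
- **Statistical analysis.** Modelling is to "compare the quality of care and survival between multidisciplinary program and controls, adjusting for measured confounders". In the model for categorical outcomes, the covariate vector "represents other confounders except matching variables". Neither statement lists the confounders.
- **Methods or procedures, Reach.** The protocol plans a description by care model: "These data will be analyzed to define the characteristics of multidisciplinary patients versus serial care patients".

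**The concern.** Patients reach the multidisciplinary clinic by referral, and the Reach component treats the kind of patient who gets there as an open question. Comorbidity can plausibly influence both that route and survival. Because it was not matched on, only the covariate list could control it, and the list in the SAP does not contain it. Sex and histology, which are also outside the protocol's matching list, were added; no reason is given for leaving comorbidity out.

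The target effect on the primary endpoint is small, a hazard ratio of 1.25. If comorbidity differs between arms within strata, part of an observed survival difference could be case mix, in either direction, and the models described would not reveal it. The planned description of patient characteristics could show an imbalance but would not correct for it.

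**Working it through.** **Text check.** Every variable in the SAP models was set against the protocol's data list. Strata: clinical stage, performance status, insurance, race, age range. Covariates: age, sex, histology. Unconditional models: the matching variables. Comorbidity is collected and appears in none of them. The plan gives no figure for comorbidity, so there is none to reproduce.

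**Inputs from the protocol (Sample size calculation; Number of subjects).** Target hazard ratio 1.25, so ln(1.25) = 0.2231; 450 patients, 150 and 300; mortality 40%, so 450 × 0.40 = 180 deaths.

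**Assumed inputs.** Prevalence of a binary comorbidity in multidisciplinary (p1) and serial (p0) patients, and its hazard ratio for death (HRc). All are taken as what remains after the strata, age, sex and histology. None is in the documents.

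**Formulas.**

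- Spurious hazard ratio, multidisciplinary versus serial: B = [1 + p1(HRc − 1)] / [1 + p0(HRc − 1)]
- Share of the target effect: |ln B| / 0.2231
- Bias in standard errors: d = |ln B| / SE
- Type I error: P(Z > 1.96 − d) + P(Z < −1.96 − d)

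The unstratified SE is √(1/(180 × 1/3 × 2/3)) = √(1/40) = 0.158. SEs of 0.20 and 0.25 illustrate the information lost to stratification. They correspond to 1/(0.20² × 2/9) ≈ 112 and 1/(0.25² × 2/9) = 72 informative deaths.

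**One case in full.** p1 = 25%, p0 = 40%, HRc = 2.0: B = 1.25/1.40 = 0.893; |ln B| = 0.1133; share = 0.1133/0.2231 = 50.8%; d = 0.1133/0.158 = 0.72; type I error = P(Z > 1.24) + P(Z < −2.68) = 11.1%.

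| p1 | p0 | HRc | B | Share of target log HR | Type I error at SE 0.158 / 0.20 / 0.25 |
|---|---|---|---|---|---|
| 40% | 40% | any | 1.000 | 0% | 5.0 / 5.0 / 5.0% |
| 30% | 40% | 1.2 | 0.981 | 8.4% | 5.2 / 5.1 / 5.1% |
| 35% | 40% | 1.5 | 0.979 | 9.4% | 5.2 / 5.1 / 5.1% |
| 30% | 40% | 1.5 | 0.958 | 19.1% | 5.8 / 5.5 / 5.3% |
| 25% | 40% | 1.5 | 0.938 | 28.9% | 6.9 / 6.2 / 5.8% |
| 30% | 40% | 2.0 | 0.929 | 33.2% | 7.6 / 6.6 / 6.0% |
| 25% | 40% | 2.0 | 0.893 | 50.8% | 11.1 / 8.8 / 7.4% |
| 40% | 25% | 2.0 | 1.120 | 50.8% | 11.1 / 8.8 / 7.4% |

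**How much imbalance is needed.** To reach a quarter of the target log hazard ratio, 0.25 × 0.2231 = 0.0558, starting from p0 = 40%, p1 must be 32.4% at HRc 2.0, 27.0% at HRc 1.5, or 10.7% at HRc 1.2. These are residual gaps of about 8, 13 and 29 points.

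**Limit of the formula.** B ignores the depletion of higher-risk patients during follow-up. The expected Cox estimate under exponential survival, 40% mortality and 1:2 arms is 0.897 instead of 0.893 in the largest case, with type I error 10.6% instead of 11.1%. The table therefore overstates the bias slightly.

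**The case against.** The strongest reply is that this is a general caveat about observational data. Stage and performance status are strata and age is a covariate, and these are the main proxies. The protocol's preliminary one-year mortality of 15%, 30% and 50% for stages I/II, III and IV shows how much of the prognosis stage alone carries. The protocol never names comorbidity as a confounder, so age, sex and histology could be read as meeting its commitment. Other collected items, such as smoking history, are also absent from the models. No document shows that comorbidity differs by arm, and every bias in the table is below one SE. The stage-appropriate treatment endpoint already allows for a documented contraindication in stages I/II and IV. Comorbidity may also be recorded more fully in the clinic, where "key specialists concurrently and directly evaluate the same patients", and a covariate recorded differently by arm can itself bias the estimate. Finally, the SAP reports its analyses in the past tense, so an added model would be post hoc.

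Much of this stands as a limit on size and certainty: the bias may be nil, the larger figures need sizeable residual imbalance, and unequal recording is a real risk. It does not remove the point. The protocol records comorbidity separately from performance status, so the proxies cannot be assumed to exhaust it. The contraindication clauses cover part of one binary endpoint, omit stage III, and do nothing for survival. A late analysis can be labelled as such.

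**Conclusion.** The point holds, as a possibility of residual confounding and not as a demonstrated bias. The models described in the SAP's Statistical Methods (Supplemental) omit a measured patient characteristic in a non-randomised comparison for which the protocol promised adjustment beyond the matching variables. One part of the SAP was not available for review, so the conclusion covers that section only.

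The effect ranges from none to moderate. It depends entirely on assumed prevalence and hazard ratios as they remain within strata, and its direction is unknown. The type I error figures at SE 0.158 are the upper end at 180 deaths, because stratification would enlarge the SE. The change is worth making: it is cheap, and the target effect is small enough for a moderate case-mix difference to matter.

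**What to change.** Build a comorbidity count or index from conditions recorded before study entry: before the first multidisciplinary visit, or before an equivalent date for serial care patients. The date of biopsy diagnosis exists in both arms and could serve as one common cut-off. Add the index to the adjusted stratified Cox model, the conditional logistic model for stage-appropriate treatment, and the unconditional companion models. Report the arm effect with and without it, and the completeness of comorbidity data by arm. If comorbidity was in fact in the models, say so. If the main analysis has already been run, label this as supplementary.

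No new data collection is expected. The cost is the work of coding the index, dating the conditions and handling missing values; the completeness of the field is not stated. The index uses a few degrees of freedom in sparse strata, so the with-and-without comparison is best read mainly in the unconditional models. The pre-entry cut-off reduces differential recording between arms but may not remove it, and this should be stated as a limitation.

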Models for survival events: All patients will be followed up for at least one year from the beginning of the study (with a median of 1.5 year). The follow up time will be longer if the starting time is retrospectively tracked back to the date of first imaging diagnosis. Assuming t_i represents the time (days) from the first imaging diagnosis to death, $h(t_i)$ is the corresponding hazard function, the proportional hazard model is $\text{log}(h(t_i)) = \beta * G_i + \gamma X_i$. The exponent of β is the hazard ratio of survival between multidisciplinary program and controls. In addition, the proportional hazard assumption in the model will be examined visually by plotting - $\text{log}(\text{log}(\text{survival}))$ and time, and also by statistically testing by adding time interaction in the model. We will also visually compare the survival curve difference using Kaplan-Meier estimate and log rank test for curve difference between two groups. Finally, the Fine-Gray competing risk model will be used to compare lung cancer specific death.

Analyses for self-reported satisfaction with care and quality of life: patient, caregiver, and provider satisfaction scores are measured using survey methods. Surveys also are used to measure quality of life, including health related quality of life and depression/anxiety (in patients and caregivers) and caregiver burden (in caregivers only). For each measure, summary scores will be calculated according to the instructions in each survey instrument. Although the scores based on Likert scales can be treated as continuous variables, we will dichotomize the satisfaction scores as satisfactory (scores 5-6 on a 6-point scale) and unsatisfactory (scores 1-4), to correspond to our benchmark criteria. Descriptive analysis and logistic model similar to the previous analyses will be used.

Potential benefits to subjects/others.

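### The survival models leave out method of detection, smoking history and comorbidities, all collected, so differences within matching strata can bias the hazard ratio in either direction

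*SAP*

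**What the plan says.** - **Endpoint.** SAP, Statistical Methods (Supplemental): "The study was designed with overall survival as the primary endpoint".
- **Data collected.** The protocol's list under Data or samples to be collected includes "method of detection" (pre-treatment care experience) and "smoking history" (patient demographics and clinical assessment). Comorbidities are on the same list.
- **Adjustment promised.** Protocol, Statistical analysis: modelling is the main tool for comparing quality of care and survival, "adjusting for measured confounders". The model equations carry a term for confounders other than the matching variables, but the protocol never lists them.
- **Adjustment specified.** The SAP describes the design as "matched by clinical stage (based on the initial diagnostic CT scan), performance status, insurance status, race, and age range". Individual 1:2 matching was then replaced by frequency matching, "with the strata now allowing multiple cases and controls per match group (frequency matching"). On covariates it says: "Models were further adjusted to include age, sex, and histology in addition to the adjustment for strata described above". The additional unconditional models are described only as entering the matching variables as covariates.
- **Time origin.** The protocol's Benchmarks/Endpoints list times survival from cancer diagnosis. Its Models for survival events section uses a time that "represents the time (days) from the first imaging diagnosis to death".

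**The concern.** Patients reach the clinic or serial care by referral, and the two groups are found by different routes: clinic patients at their first clinic visit, serial patients from code-based and treating-group lists. The protocol's Reach section treats the difference in case mix as an open question. Covariate adjustment therefore has to carry much of the comparison, and more of it once individual matching was given up.

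Method of detection bears directly on the primary endpoint. A tumour found by screening or by chance starts its survival clock earlier than a symptomatic one, whether the clock runs from diagnosis or from first imaging. It may also grow more slowly than a symptomatic tumour of the same stage. Smoking and comorbidity act differently, as ordinary prognostic factors. If any of the three differs between arms within a stratum, the fitted hazard ratio mixes that difference with the effect of the care model. The mix could favour either arm.

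**Working it through.** **Coverage of each factor**

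| Factor | Collected (protocol) | Matching variable | Covariate in SAP models |
|---|---|---|---|
| Method of detection | yes | no | no |
| Smoking history | yes | no | no |
| Comorbidities | yes | no | no |
| Age | yes (date of birth) | yes (age range) | yes |
| Sex, histology | yes | no | yes |

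**Size of the possible bias.** The plan gives no figure for this, so there is none to reproduce. From the documents: design hazard ratio 1.25, 450 patients, 40% mortality, 1:2 allocation. Assumed, because the documents are silent: prevalence of each factor by arm, and its hazard within strata.

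For a binary factor with hazard *h* relative to other patients in the same stratum, and prevalence *pM* (multidisciplinary) and *pS* (serial), the hazard ratio with no true effect is approximately

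HR = (*pM*·*h* + 1 − *pM*) / (*pS*·*h* + 1 − *pS*).

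Stronger hazards:
- Early detection 20% v 10%, *h* = 0.6: 0.92/0.96 = 0.958.
- Early detection 30% v 10%, *h* = 0.6: 0.88/0.96 = 0.917.
- Current smoking 40% v 50%, *h* = 1.4: 1.16/1.20 = 0.967.
- Combined: 0.958 × 0.967 = 0.93 and 0.917 × 0.967 = 0.89.

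Same imbalances reversed between arms: 1/0.93 = 1.08 and 1/0.89 = 1.13, using unrounded values.

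Weaker hazards, same prevalences:
- Detection, *h* = 0.8: 0.96/0.98 = 0.980 and 0.94/0.98 = 0.959.
- Smoking, *h* = 1.2: 1.08/1.10 = 0.982.
- Combined: 0.96 and 0.94.

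Equal prevalence in both arms gives exactly 1. Comorbidity is not in this arithmetic; it could add to the bias or offset it.

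**Against the design effect.** A hazard ratio of 1.25 for serial v multidisciplinary care is 1/1.25 = 0.80 the other way round, so the planned log effect is 0.223. The stronger-hazard biases are 0.076 and 0.121 on the log scale, or 34% and 54% of it. The weaker ones are 0.039 and 0.060, or 17% and 27%.

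**Against sampling error.** Expected deaths are 450 × 0.40 = 180. At 1:2 allocation, SE(log HR) = 1/√(180 × 1/3 × 2/3) = 1/√40 = 0.158. The stronger-hazard biases are then 0.076/0.158 = 0.5 and 0.121/0.158 = 0.8 standard errors. The two-sided 5% test would reject a true null about 8% to 12% of the time.

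**Cross-check treating early detection as a clock shift.** Take a constant hazard giving 40% mortality at 18 months, −ln(0.6)/18 = 0.0284 per month. Assume a six-month lead time in 10% of serial patients and in 20% or 30% of clinic patients. Deaths per person-month over 18 months give serial-to-multidisciplinary ratios of 1.044 and 1.092, or 0.96 and 0.92 the other way round. These are close to the detection figures above. A three-month lead time roughly halves the log bias and a twelve-month one roughly doubles it.

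**The case against.** **The size is assumption throughout.** This stands. No document gives detection mode, smoking or comorbidity by arm, or a hazard within strata. A hazard of 0.6 is strong for what is left after stage, performance status and histology. Multiplying the two factors also assumes that both imbalances point the same way. Hence the reversed and weaker cases.

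**The design already absorbs part of this.** This stands in part. Early detection shows largely as earlier stage and better performance status, both of which are stratified, and histology is a covariate. Both arms need untreated, biopsy-confirmed cancer in the same system, preferably diagnosed within a close window. Only the difference within strata is at issue, but lead time and smoking-related prognosis can persist there.

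**A covariate is an imperfect remedy for lead time.** This stands. Lead time shifts the clock rather than scaling the hazard, so a proportional-hazards term corrects it only approximately. The conflict between the two time origins is also not resolved by any covariate.

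**Part of the request is already planned.** The protocol's Reach section commits to describing the two groups' characteristics, so tabulation by arm adds little work. It does not replace adjustment.

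**The SAP is in the past tense, so a change would be post hoc.** This bears on labelling, not on substance. A declared sensitivity analysis meets it.

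Three stronger readings are not supported:
- That a survival advantage for the clinic would be an artefact. The direction is unknown and the distributions may be equal.
- That the SAP breaks a prespecified covariate list. The protocol gives none, so the SAP narrows a general commitment.
- That the binary endpoints need the same change. The lead-time argument concerns survival only.

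**Conclusion.** The concern holds as a gap in confounder control for the primary endpoint. Three measured prognostic factors appear in no specified model of a non-randomised comparison, although the protocol promises adjustment for measured confounders.

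The possible bias is moderate under the assumed inputs: a null hazard ratio of about 0.89–0.93, or 1.08–1.13 with the imbalances reversed, and about 0.94–0.96 with weaker hazards. The stronger cases amount to roughly a third to a half of the planned log effect, yet remain below one standard error at 180 deaths. The prevalences and hazards are not in the documents, and equal distributions give no bias. The documents therefore show that bias is possible, not that it is present or which arm it favours. The conclusion rests on the model description in the SAP's Statistical Methods (Supplemental).

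**What to change.** In the SAP's Statistical Methods (Supplemental):

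1. Add method of detection, smoking history and comorbidities, each with an unknown level, to the stratified and unconditional Cox models for overall survival.
2. Report the hazard ratio with and without them. If the primary model is already fixed, present the extended model as a labelled sensitivity analysis.
3. Tabulate the three variables by arm.
4. State that this adjustment reduces lead-time bias but does not remove it.
5. Separately, reconcile the two time origins in the protocol (diagnosis in Benchmarks/Endpoints, first imaging in Models for survival events).

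No new data are needed. Detection and smoking use about three or four model degrees of freedom, and comorbidity adds some according to its coding, against about 180 expected deaths. Some precision is lost. The stratified model has less information than 180 deaths suggests, because strata containing only one arm contribute nothing to the comparison of care models.
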